9.7.6.1 Adverse Events

For patients who completed the lead-in study (VLZ-MD-22), an AE (classified by preferred term) that occurs during the open-label treatment period or during the down-taper period will be considered a treatment-emergent adverse event (TEAE) if it was not present before the date of the first dose of double-blind investigational product in the lead-in study or if it was present before the date of the first dose of double-blind investigational product in the lead-in study and increased in severity during the open-label treatment period or during the down-taper period. If more than 1 AE is reported before the date of the first dose of double-blind investigational product in the lead-in study and coded to the same preferred term, the AE with the greatest severity will be used as the benchmark for comparison with the AEs occurring during the treatment period or during the down-taper period that were also coded to that preferred term. An AE that occurs more than 30 days after the date of the last dose of investigational product will not be counted as a TEAE.

For *de novo* patients, an AE (classified by preferred term) that occurs during the open-label treatment period or during the down-taper period will be considered a TEAE if the AE was not present before the date of the first dose of open-label investigational product or if it was present before the date of the first dose of open-label investigational product and increased in severity during the open-label treatment period or during the down-taper period,. If more than 1 AE is reported before the date of the first dose of open-label investigational product and coded to the same preferred term, the AE with the greatest severity will be used as the benchmark for comparison with the AEs occurring during the open-label treatment period or during the down-taper period that were also coded to that preferred term. An AE that occurs more than 30 days after the date of the last dose of investigational product will not be counted as a TEAE.

An AE occurring during the down-taper period will be considered a newly emergent adverse event (NEAE) if it was not present before the start of the down-taper period or was present before the start of the down-taper period but increased in severity during the down-taper period. An AE that occurs more than 30 days after the date of the last dose of investigational product will not be counted as a NEAE.

NEAEs reported during the down-taper period will be summarized separately by body system and preferred term.

The number and percentage of patients reporting TEAEs during the open-label treatment period and during the down-taper period will be tabulated separately by system organ class, preferred term, and causal relationship to the investigational product. If more than 1 AE is coded to the same preferred term for the same patient, the patient will be counted only once for that preferred term using the most severe and most related occurrence for the summarization by severity and by causal relationship to the investigational product.

The distribution of TEAEs by severity and causal relationship to the investigational product will be summarized separately for the open-label treatment period and the down-taper period.

The incidence of common ($\geq 2\%$ of patients) TEAEs during the open-label treatment period will be summarized separately by preferred term.

An SAE that occurred between the date of the first dose of open-label investigational product and 30 days after the date of the last dose of open-label investigational product in the study, inclusive, will be considered an on therapy SAE. The incidence of SAEs and AEs leading to premature discontinuation of the study will also be summarized by study period, system organ class and preferred term. Listings will be presented for patients with SAEs, patients with AEs leading to premature discontinuation, and patients who died. All patients with SAEs, including those reported during the screening period or more than 30 days after the date of the last dose of the open-label investigational product, and patients discontinuing due to AEs before the start of open label investigational product will be included in these listings.

Listings will be presented for patients with SAEs, patients with AEs leading to discontinuation, and patients who die (if any).

9.7.6.2 Clinical Laboratory Parameters

Descriptive statistics for clinical laboratory values (in SI units) and changes from the baseline values at each assessment time point will be presented for each clinical laboratory parameter.

The number and percentage of patients with potentially clinically significant (PCS) postbaseline clinical laboratory values will be tabulated. The criteria for PCS laboratory values will be detailed in the statistical analysis plan. The percentages will be calculated relative to the number of patients with available non-PCS baseline values and at least 1 postbaseline assessment. The numerator will be the total number of patients with available non-PCS baseline values and at least 1 PCS postbaseline value. A supportive listing of patients with PCS postbaseline values will be provided, including the PID number, study center number, and baseline and postbaseline values. A listing of all AEs that occur in patients who have PCS laboratory values will also be provided.

9.7.6.3 Vital Signs

Descriptive statistics for vital signs (ie, sitting radial pulse rate, sitting systolic and diastolic BP, body weight, and height) and changes from baseline values at each visit and at end of study will be presented. In addition, height and weight z scores will be calculated based on growth charts (see Section 9.7.6.5.2).

Vital sign values will be PCS if they meet both the observed-value criteria and the change-from-baseline value criteria. The criteria for PCS vital sign values will be detailed in the Statistical Analysis Plan. The percentages will be calculated relative to the number of patients with baseline values and at least 1 postbaseline assessment. The numerator will be the total number of patients with available baseline values and at least 1 PCS postbaseline value. A supportive listing of patients with PCS postbaseline values will be provided, including the PID number, study center number, and baseline and postbaseline values. A listing of all AEs that occur in patients who have PCS vital sign values will also be provided.

9.7.6.4 Electrocardiograms

Descriptive statistics for ECG parameters (ie, ventricular heart rate, RR interval, PR interval, QRS interval, QT interval, and QTc) and changes from baseline values at each assessment time point will be presented. The QTc is calculated using both the Bazett and Fridericia corrections.

The number and percentage of patients with PCS postbaseline ECG values will be tabulated. The criteria for PCS ECG values will be detailed in the statistical analysis plan. The percentages will be calculated relative to the number of patients with available non-PCS baseline values and at least 1 postbaseline assessment. The numerator will be the total number of patients with available non-PCS baseline values and at least 1 PCS postbaseline value. A supportive listing of patients with PCS postbaseline values will be provided, including the PID number, study center number, and baseline and postbaseline values. A listing of all AEs that occur in patients who have PCS ECG values will also be provided.

A listing of patients with postbaseline clinically significant ECG abnormalities, as reported by the Investigator or by the central cardiologist, will also be provided.

The number and percentage of patients with an increase > 30 msec but ≤ 60 msec, and with an increase > 60 msec in QTcB or QTcF will be tabulated. A supportive listing of patients with postbaseline QTcB or QTcF increases > 30 msec will be provided, including the PID number, study center number, and all QTcB and QTcF values (including changes from baseline). A listing of all AEs that occur in patients who have postbaseline QTcB or QTcF increases > 30 msec will also be provided.

9.7.6.5 *Other Safety Parameters*

9.7.6.5.1 *Columbia–Suicide Severity Rating Scale*

For the C-SSRS, the number and percentage of patients with suicidal ideation or suicidal behavior as recorded on the C-SSRS scale will be presented. The distribution of responses for most severe suicidal ideation and suicidal behavior during the lifetime history, the open-label treatment period, and the down-taper period will also be presented for the Safety Population. Supportive listings will be provided and will include the PID number, visit number, lifetime history, and postbaseline values for each patient. Intensity of ideation, suicidal behavior type, and lethality of suicidal behavior will also be included in these listings.

9.7.6.5.2 *Growth Evaluation*

Weight and height will be presented as standardized z scores adjusted for gender and age, using the lambda-mu-sigma method ([Cole, 1990](#)).

9.7.6.6 *Investigational Product Plasma Concentration Parameters*

Not applicable

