9.3.3 Removal of Patients from Therapy or Assessment

A premature discontinuation will occur when a patient who gave voluntary assent and/or whose LAR signed the ICF ceases participation in the study, regardless of circumstances, before the completion of the study visits and procedures. Patients can be prematurely discontinued from the study for any of the following reasons:

- Failure to meet inclusion/exclusion criteria
- Withdrawal of assent or consent (a reason must be documented)
- Adverse event (AE)

- Worsening of MDD symptoms or insufficient therapeutic response
- Protocol deviation, including lack of compliance
- Lost to follow-up (every effort must be made to contact the patient; at least 2 documented telephone calls must be made and 2 registered letters must be sent)
- Study or study center prematurely terminated by FRI for any reason
- Other reasons, such as specified administrative reasons or pregnancy

All enrolled patients who prematurely discontinue from the study, regardless of cause, should be seen for a final assessment at an Early Termination (ET) Visit. A final assessment will be defined as completion of the evaluations scheduled for all patients at the end of Week 26 (Visit 16). All patients discontinuing the study prematurely should enter the 1-week down-taper period when clinically appropriate.

Patients who discontinue from the study and do not return to the study center for final assessments must be requested in writing to return to the study center for a final assessment and return any unused investigational product. A copy of the letter, together with the source documentation, will be kept in the Investigator's files. The reason for premature discontinuation from the study will be recorded on the Study Termination Page of the eCRF. Study center staff will be contacted by FRI after each premature discontinuation to ensure proper characterization of the reason for discontinuation is captured.

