9.5.2.12.2 Columbia–Suicide Severity Rating Scale

The Columbia–Suicide Severity Rating Scale (C-SSRS) is an instrument that reports the severity of both suicidal ideation and behavior. Suicidal ideation is classified on a 5-item scale: 1 (wish to be dead), 2 (nonspecific active suicidal thoughts), 3 (active suicidal ideation with any methods [not plan] without intent to act), 4 (active suicidal ideation with some intent to act, without specific plan), and 5 (active suicidal ideation with specific plan and intent). The C-SSRS also captures information about the intensity of ideation, specifically the frequency, duration, controllability, deterrents, and reasons for the most severe types of ideation. Suicidal behavior is classified on a 5-item scale: 0 (no suicidal behavior), 1 (preparatory acts or behavior), 2 (aborted attempt), 3 (interrupted attempt), and 4 (actual attempt). More than 1 classification can be selected provided they represent separate episodes. For actual attempts only, the actual or potential lethality is classified for the initial, most lethal, and most recent attempts.

The paper version of the C-SSRS will be completed at all study visits. At Screening (Visit 1) the C-SSRS will be completed for the patient's lifetime history of suicidal ideation and behavior for *de novo* patients only; for rollover patients, patient's lifetime history of suicidal ideation and behavior data will be copied from Visit 1 in Study VLZ-MD-22 and kept with patients' source documents for this study. At all other visits, the C-SSRS will be completed for ideation and behavior since the previous visit ([Appendix VIII](#)). The C-SSRS will be evaluated and signed at each visit by a qualified staff member (ie, the Investigator or designee that has extensive professional training and experience in assessing mental illness) before the patient leaves the study center.

The patient should not be released from the study center until the results of the C-SSRS are reviewed and the patient is not considered to be at risk. If there is doubt about whether a patient is at risk, the Investigator must obtain appropriate psychiatric consultation. The results of the C-SSRS will be recorded in the eCRF. A copy of the C-SSRS is provided in [Appendix VII](#).

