11.5.1 Suicidality Assessment

For the C-SSRS, the number and percentage of patients with any suicidal ideation or suicidal behavior will be presented by cohort, separately for the lifetime history, the open-label treatment period and the open-label down-taper period. The distribution of responses for the most severe suicidal ideation and suicidal behavior will be summarized by cohort and by lead-in treatment group, separately for the lifetime history, the open-label treatment period, and the open-label down-taper period. Supportive listings will be provided and will include the patient identification number, treatment group, visit number, lifetime history, and postbaseline values for each patient. Intensity of ideation, suicidal behavior type, and lethality of suicidal behavior will also be included in these listings. A listing of all AEs occurring in patients who have suicidal ideation or suicidal behavior will also be provided.

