16.4 REPEATED OR UNSCHEDULED ASSESSMENTS OF SAFETY PARAMETERS

For roll-over patients, the corresponding baseline of the double-blind lead-in study will be used. If a de novo patient has repeated assessments before the date of the first dose of open-label investigational product, the results from the final nonmissing assessment made before the date of the first dose of open-label investigational product will be used as baseline. If the end-of-open-label-treatment period assessments are repeated or if unscheduled visits occur, the last nonmissing postbaseline assessment during the open-label treatment period will be used as the end-of-open-label-treatment-period assessment for generating summary statistics. Likewise, if the end of open-label down-taper period assessments are repeated or if unscheduled visits occur, the last non-missing assessment during the open-label down-taper period will be used as the end-of-open-label-down-taper-period assessment for generating summary statistics. However, all postbaseline assessments will be used to determine PCS values for laboratory parameters, vital signs and ECG parameters, and to determine most severe suicidal ideation and most severe suicidal behavior from C-SSRS. All assessments will be presented in the data listings.

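### Suicidality is counted only from C-SSRS forms completed at visits, so a suicide or attempt with no later form is absent from the suicidality tables, and no planned output counts patients across the C-SSRS and the AE, SAE and death records.

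*Protocol*

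**What the plan says.** **Source of the counts.** Protocol 9.7.6.5.1 plans that the "number and percentage of patients with suicidal ideation or suicidal behavior as recorded on the C-SSRS scale will be presented". SAP 11.5.1 follows: "For the C-SSRS, the number and percentage of patients with any suicidal ideation or suicidal behavior will be presented by cohort". SAP 16.4 uses all postbaseline assessments, including repeated and unscheduled ones, "to determine most severe suicidal ideation and most severe suicidal behavior from C-SSRS". In the visible text, no AE, SAE or death record feeds these counts.

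**The scale.** Protocol 9.5.2.12.2 states: "Suicidal behavior is classified on a 5-item scale: 0 (no suicidal behavior), 1 (preparatory acts or behavior"; it ends at "3 (interrupted attempt), and 4 (actual attempt". It gives no level for completed suicide.

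**When a form exists.** The same section has the C-SSRS completed at study visits, with recall back to the previous visit. Protocol 9.5.2 says safety assessments should not be done without the consented caregiver. Protocol 9.5.5.17 leaves the content of unscheduled visits to the investigator. Protocol 9.3.3 foresees non-return: "Patients who discontinue from the study and do not return to the study center for final assessments must be requested in writing".

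**Other reporting of the same events.** Protocol 9.7.6.1 and SAP 11.1 tabulate TEAEs and SAEs by system organ class and preferred term, and list SAEs, AEs leading to discontinuation, and deaths. SAEs count as on-therapy up to 30 days after the last dose.

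**The one cross-link.** SAP 11.5.1: "A listing of all AEs occurring in patients who have suicidal ideation or suicidal behavior will also be provided".

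**The concern.** The protocol's introduction cites suicidality as the class risk behind the boxed warning, and section 9.10 names it as an example of what the Data Monitoring Committee is to watch. A reader of the study report will take the suicidality rate from the C-SSRS tables.

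Those tables depend on the patient coming back and a form being completed. The gravest events are the ones most likely to prevent that. The protocol's scale also has nowhere to put a completed suicide. The tables could then show no suicidal behavior for a patient who appears in the death listing as a suicide. Any such error runs in one direction, towards too few cases.

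**Working it through.** The plan states no figure on this point and has no inferential analysis, so there is nothing to reproduce. The check follows the counting rule through the possible cases and then sizes one case.

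**1. Tracing the rule**

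| Situation | C-SSRS tables | AE, SAE and death outputs |
|---|---|---|
| Attempt; patient later attends a visit with a form | Counted, because recall reaches back to the previous visit | Reported |
| Earlier forms all 0; then an attempt with no later form | Stays at behavior 0 | Reported by preferred term |
| Earlier forms all 0; then suicide | Stays at behavior 0 | SAE and death outputs |
| Earlier form positive for ideation only; then an attempt or suicide with no later form | In the ideation count; behavior stays 0 | Reported, and in the cross-linked AE listing |
| No postbaseline form; event occurs | Not stated whether shown as 0 or missing | Reported |
| Event after the last visit, within 30 days of last dose | Not captured unless a further visit includes a form | On-therapy SAE if serious; if not serious, in the eCRF only if judged possibly related (Protocol 9.5.2.5) |

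The gap is therefore limited to events with no later form: death, permanent non-return, a visit without a form, or the period after the last visit. The AE listing in SAP 11.5.1 starts from patients who already have ideation or behavior, so it cannot find a patient whose C-SSRS is negative or absent.

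**2. Size of one case**

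Inputs: N = 315 (Protocol 9.1.2) and N = 250 (SAP 14.0, in a plan that cites the 15 Dec 2014 protocol). Each missed patient lowers the percentage by 100/N:

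- 100/315 = 0.32 points
- 100/250 = 0.40 points

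**3. Illustration for behavior**

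Suppose the C-SSRS table shows no patient with behavior and k patients are known only from AE, SAE or death reports. The values of k are assumptions. The exact 95% intervals are for scale only.

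| k | k/315 | k/250 |
|---|---|---|
| 0 | 0% (0 to 1.16) | 0% (0 to 1.46) |
| 1 | 0.32% (0.01 to 1.76) | 0.40% (0.01 to 2.21) |
| 2 | 0.63% (0.08 to 2.27) | 0.80% (0.10 to 2.86) |
| 3 | 0.95% (0.20 to 2.76) | 1.20% (0.25 to 3.47) |

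**4. Illustration for ideation or behavior combined**

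Protocol 7.0 quotes 4% on antidepressants. That figure comes from placebo-controlled trials, not from 26 weeks of C-SSRS forms, so it sets a scale and is not a forecast. At N = 315, 0.04 × 315 = 12.6, or about 13 patients (13/315 = 4.1%). If 1, 2 or 3 of them were missed, the table would show 12/315 = 3.8%, 11/315 = 3.5% or 10/315 = 3.2%. At N = 250, 10 patients (4.0%) would become 3.6%, 3.2% or 2.8%.

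**5. Chance that at least one such case occurs**

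With an assumed per-patient chance p, this is 1 − (1 − p)^N. For p = 0.25%, 0.5% and 1% the result is 55%, 79% and 96% at N = 315, and 47%, 71% and 92% at N = 250. The documents give no value for p.

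**The case against.** The strongest reply is that nothing is hidden. A suicide or attempt appears in the TEAE and SAE tables and in the SAE and death listings, which include SAEs more than 30 days after the last dose. The C-SSRS tables are labelled as summaries of one instrument, and their listings carry patient identifiers that can be matched by hand. This stands: a reader who inferred that such events vanish from the report would be wrong. What it does not supply is a count. Preferred-term rows split related events, and no planned output removes duplicates between them and the C-SSRS.

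A second reply is that the plan works hard to obtain a last form. Patients who discontinue should have an early termination visit with the Week 26 evaluations, Visit 17 is required of all enrolled patients, and extra follow-up visits are allowed. This also stands. It would be wrong to infer that a patient hospitalised after an attempt is generally missed, because the next form captures the event if the patient returns.

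Third, some material cannot be seen. Only the cover text of the C-SSRS appendices is visible, so it cannot be said that the form itself lacks a completed-suicide item; the ceiling rests on the protocol's own description of the scale. Table and listing specifications are in a separate document, SAP 16.8 and 16.9 are not shown, and the Data Monitoring Committee charter is not available. The point is therefore about the visible protocol and SAP text.

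Finally, data after the final visit are thinner, since nonserious AEs judged unrelated stay in source documents. A combined count to 30 days after the last dose would mix two recording rules. This is a fair limit on the remedy and should be footnoted. Fatal events are serious by definition and still reach the eCRF.

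**Conclusion.** The point holds in a limited form. The suicidality tables omit any attempt or suicide with no later C-SSRS form. A patient with earlier zero scores then remains at no suicidal behavior, and no planned output gives a de-duplicated number of patients with suicidality from either source. The bias can only be downward, and it falls on the most serious events.

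The number of patients concerned is unknown. Each one is worth 0.32 points at 315 patients or 0.40 at 250. The shift is small in absolute terms, but it matters where the behavior count itself is likely to be a handful. Nothing in the documents supports a claim that a particular fraction of cases would be lost. Nor do they support treating a patient with no postbaseline form as a recorded zero; the plan does not say how such a patient is shown.

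This is an inexpensive improvement that should be made in a safety study, not a flaw that undermines it.

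**What to change.** Keep the C-SSRS tables as instrument summaries and add the following to SAP 11.5.1:

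- A patient-level table with three rows: C-SSRS only; AE, SAE or death only; and either source. Identify the second source by a prespecified MedDRA search for suicide and self-injury terms, from first open-label dose to 30 days after last dose.
- Completed suicide as a separate top row.
- A listing of every patient for whom the two sources disagree.
- A statement of the denominator and of how patients with no postbaseline form are shown.
- A footnote that, after the final visit, only AEs that are serious or judged possibly related are recorded in the eCRF.

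The cost is some SAP wording, one table and one listing, all from data already in the eCRF. No new data collection is needed. The reported rate may come out slightly higher.
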